1.0 OBJECTIVES

The overall objective is to determine whether the natural flaxseed lignan, secoisolariciresinol diglycoside (SDG), in amounts providing plasma lignan levels associated with reduced breast cancer risk, will favorably modulate risk biomarkers for breast cancer development. This will provide biologic evidence of SDG's potential for breast cancer chemoprevention. Based on a positive pilot study in which both Ki-67 and the proportion of women with atypical cytomorphology was reduced with 12 months of SDG 50 mg/day, a randomized, placebo-controlled clinical chemoprevention trial will be conducted wherein pre-menopausal women at increased risk for the development of breast cancer will receive Brevail® (200 mg, equivalent to 50 mg of SDG) or matched, blinded placebo for 12 months. A total of 242 subjects will be accrued, randomized 2:1 to SDG vs placebo, with the goal of achieving 220 subjects completing study and evaluable for biomarker change.

The primary objective is to determine if women randomized to 12 months of SDG exhibit greater change in the proportion of breast epithelial cells expressing the proliferation marker Ki-67/MIB-1 in hyperplastic benign breast tissue than do women randomized to placebo.

Secondary objectives are:

- 1) to determine if 12 months of SDG is associated with favorable modulation of other risk biomarkers including cytologic atypia, and serum levels of bioavailable estradiol and testosterone, IGF-I:IGFBP-3 ratio, c-peptide, adiponectin, and leptin.
- 2) to determine if Ki-67 and modulation of other risk biomarkers is correlated with change in blood or urine lignans.
- 3) to determine impact or potential impact on quality of life as measured by the BPQ breast pain questionnaire (a modified McGill Pain questionnaire), The Breast Cancer Prevention Trial (BCPT) Symptom Checklist a menstrual diary for cyclicity and cycle length for women not on cycle modulating contraceptives; and antimullerian hormone (AMH), a measure of follicular reserve.

An exploratory objective is to interrogate SDG's mechanism of action through measurement of changes in hormones, growth factors, gene expression, adipokines and cytokines and proteomic signatures.

The overriding hypothesis is that biomarkers assessed both in serum and in hyperplastic breast tissue obtained by RPFNA from high risk pre-menopausal women will be favorably modulated by 12 months of SDG without negatively affecting quality of life.

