2.4.3 Eligibility criteria for SDG pilot study

Eligibility criteria included regular menstrual cycles, no oral contraceptives, a 3-fold or greater increase in 5-year estimated risk for breast cancer relative to SEER statistics for age group, and normal mammogram performed in the follicular phase of the menstrual cycle within 3 months of baseline RPFNA. Subjects on oral contraceptives were excluded in order to reduce subject hormonal heterogeneity and because it might be more difficult to demonstrate biomarker modulation from SDG in the face of exogenous hormones. Baseline RPFNA was also to be performed in the follicular phase and had to show unequivocal hyperplasia +/- atypia as well as a minimum Ki-67 expression of 2% in hyperplastic ducts. The Ki-67 value of 2% was chosen since this is the median Ki-67 value in hyperplastic tissue obtained by RPFNA from high risk pre-menopausal women in the follicular phase of the cycle [86]. Further, a Mayo Clinic series suggests that women having a biopsy showing atypical hyperplasia and a Ki-67 of 2% or higher have a significantly higher 10-year risk of breast cancer (14% versus 3%) [88]. The early-mid follicular phase is utilized due to greater subject comfort and less bleeding during RPFNA.

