2.4.4.2. Change in Ki-67 and cytomorphology

Thirty-six (80%) of the 45 evaluable subjects demonstrated a decrease in Ki-67, from a median of 4% (range 2-16.8%) to 2% (range 0-15.2%) ($p<0.001$ by Wilcoxon signed rank test). A decrease from baseline in the proportion of women with atypical cytology from 62% to 42% ($p=0.035$) was also observed.

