4.6 ID Assignment and Randomization

4.6.1 Each site will have a series of unique study IDs that provide the study agent assignment. The site study coordinator will assign the subject the next available sequential study ID. All forms, questionnaires and biospecimens subsequent to randomization are to be labeled with this study ID as well as the date.

4.6.2 Each site investigational pharmacy will have a randomization schedule which has been prepared and provided by the Study Statistician. Study agent randomization to placebo or active SDG will be provided for each sequential post-randomization study ID number. Other than the investigational pharmacist(s) and the central biostatisticians, the enrolling site staff, the coordinating site staff, and subjects will be blinded as to the assignment to active agent or matched placebo.

4.6.3 For subjects not on oral contraceptives, sequential study ID numbers are assigned starting at X001 and then increasing (e.g., X002, X003, etc.). Subjects using oral contraceptives will be assigned a study ID number starting with the last number provided to the institution and then in decreasing order (e.g., X099, X098, X097, etc.).

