11.1 Sample Size and Power

The primary outcome of interest is efficacy of SDG relative to the placebo, thus the pre- to post-treatment change in a proliferation index (percent of cells expressing Ki-67) is the basis of the power analyses. From our pilot study, the average percentage of cells expressing Ki-67 at baseline was 4%, and the average change in percent of cells expressing Ki-67 was a 2.4% reduction, for subjects meeting similar eligibility requirements as used in this trial.

A 2:1 randomization of 220 evaluable subjects will provide 83% power to detect a 2.5% reduction in Ki-67 for the treatment group compared to no reduction in the control group; this will be our primary endpoint. This is based on an assumption of a common standard deviation of 6% for change in Ki-67 in both groups and a Type I error rate of 5%. Within the target of 220 evaluable subjects, we expect to recruit 72 women taking oral contraceptives (OC) and 148 women not taking OCs. Because the efficacy of SDG is unknown for OC users, we considered different scenarios and evaluated the average effect in the SDG arm and the corresponding power. For 0-70% efficacy of SDG among OC users, the respective average Ki-67 reduction range from 1.7% to 2.3% will result in a statistical power ranging from 50% to 76%.

Ki-67 reduction in SDG arm (non-OC)	Efficacy of SDG in OC	Ki-67 reduction in SDG arm (OC)	Ki-67 reduction in SDG arm (OC & non-OC avg.)	Power
2.5%	0%	0%	1.7%	50%
2.5%	20%	0.5%	1.8%	55%
2.5%	50%	1.3%	2.1%	68%
2.5%	70%	1.8%	2.3%	76%
2.5%	100%	2.5%	2.5%	83%

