11.2 Statistical Analysis

All analyses will be intent-to-treat. All subjects randomized will be evaluable for safety and all subjects that have both a pre and post specimen are evaluable for efficacy. Primary analysis of efficacy will be performed on all evaluable subjects and secondary analysis will be done on those subjects who received at least 6 months of study medication and were confirmed as being in the follicular phase for both RPFNA procedures. From our experience we have very little missing data; however, if the missing data rate is above 5%, we will use multiple imputation to impute these values to perform the primary and secondary analyses.

The primary outcome will be change in Ki-67 (percent of cells expressing Ki-67) from baseline to 12 months. The two-sample t-test will be used to compare the change in Ki-67 between the SDG

and placebo groups. Any difference in baseline values of Ki-67 between the two groups would be due to chance, however, if there is a significant difference, then analysis of covariance adjusting for baseline values will be performed. Due to potential skewness in these variables we will assess whether or not the Central Limit Theorem may be assumed. Given the sample size the existence of an extremely high degree of skewness would require the use of the Wilcoxon Signed Rank test.

For the secondary endpoints, similar methods as above will be used to compare the treatment and control groups at two time points for all markers, i.e., serum hormones and clinical laboratory tests. We will also correlate change in the primary biomarker Ki-67 with change in other markers (e.g., bioavailable estradiol, cytokines, RTqPCR results) using Pearson's correlation coefficient. Again, if there exists a high degree of skewness in these variables, Spearman's correlation will be utilized.

Multiple regression analysis will also be used to investigate whether changes in Ki-67 are due to variables other than treatment effect (e.g., age, cytromorphology, Gail risk; as well as the predictive effect of other biomarkers on modulation of Ki-67). Best subsets and stepwise approaches will be employed while controlling for treatment group.

For comparison of moderate or worse toxicities we will consider grade 3 toxicity or premature trial discontinuation as the critical events. The prevalence of events in the SDG vs. the placebo arm will be examined by Fisher's exact test.

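### The fallback for skewed Ki-67 change names the Wilcoxon signed-rank test, which cannot compare SDG with placebo

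*Combined protocol and SAP*

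**What the plan says.** Section 1.0 sets a between-arm question: whether women on SDG show a greater change in Ki-67 "in hyperplastic benign breast tissue than do women randomized to placebo". Section 11.1 repeats it: "The primary outcome of interest is efficacy of SDG relative to the placebo". Section 11.2 follows with a suitable default: "The two-sample t-test will be used to compare the change in Ki-67 between the SDG" and placebo groups. The same paragraph allows for skewness by asking whether the Central Limit Theorem can be relied on, and then gives the fallback: "Given the sample size the existence of an extremely high degree of skewness would require the use of the Wilcoxon Signed Rank test". No numerical criterion for skewness is stated.

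For the secondary endpoints, section 11.2 says "similar methods as above will be used to compare the treatment and control groups at two time points for all markers", so the fallback carries over to them.

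The only other mention of this test is in section 2.4.4.2, where the single-arm pilot's before-and-after change was assessed "by Wilcoxon signed rank test". It was appropriate there. Neither the rank-sum nor the Mann-Whitney test is named in the document.

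**The concern.** The signed-rank test takes one set of differences and asks whether they are symmetric about zero. It has no term for treatment arm. It cannot be turned into a paired comparison of SDG with placebo, because the arms are independent and, at 2:1 among 220 evaluable women, unequal (about 147 and 73). It also assumes symmetric differences, which is the condition that its trigger says has failed.

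If the fallback is invoked, one of two things follows.

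- **A substitute is chosen once data exist.** Section 4.6.2 lists who is blinded with the exception "Other than the investigational pharmacist(s) and the central biostatisticians", so the people choosing may not be blinded.
- **The test is run literally within the SDG arm.** Entry requires Ki-67 of at least 2% (section 4.4.3), and section 2.4.3 says of that cut-off: "The Ki-67 value of 2% was chosen since this is the median Ki-67 value in hyperplastic tissue". Women chosen for being above the median will tend to be lower on repeat sampling with no drug effect. A within-arm test counts that fall as efficacy. A comparison with placebo removes it.

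**Working it through.** **1. What each test uses.** Let d be a woman's change in Ki-67. The signed-rank statistic is the sum of the ranks of |d| over women with d > 0 in one group. The rank-sum (Mann-Whitney) statistic counts pairs of one SDG and one placebo woman in which the SDG woman has the larger d. Only the second refers to both arms.

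**2. The plan's own figure.** Inputs from sections 11.1 and 11.2: 220 evaluable, 2:1, difference 2.5, SD 6, two-sided 5%.

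- Standard error = 6 × √(1/146.67 + 1/73.33) = 0.858
- Difference / standard error = 2.5 / 0.858 = 2.913
- Power = Φ(2.913 − 1.960) = Φ(0.953) = 83.0%

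The noncentral t with 147 and 73 women gives 82.6%. The stated 83% reproduces, and it belongs to a between-arm test.

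**3. What the signed-rank test responds to.** Suppose both arms fall by the same amount, so SDG adds nothing. Take normal changes with SD 6. The approximate rejection rate in the SDG arm is Φ(√(3/π) × fall × √147 / 6 − 1.960).

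- Common fall 2.4 (the pilot mean change in section 11.1; section 3.0 gives 3.7): Φ(0.977 × 4.850 − 1.960) = Φ(2.78) = 99.7%. Simulation (4,000 trials) gives 99.7%, against 4.9% for rank-sum and 5.0% for the t-test.
- Common fall 1.0: simulation gives 50.6%, against 5.3% for rank-sum.

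**4. Falls produced by selection alone.** Assumed model with no drug effect: Ki-67 is lognormal, the unselected median is 2% (section 2.4.3), women enter at 2% or more, and the selected median is 4% (section 2.4.4.2). The log-SD is then ln 2 / 0.6745 = 1.03. The test-retest correlation on the log scale is not in the documents, so a range is shown. There are 10,000 trials per value with 147 SDG and 73 placebo women. The third row requires sample skewness beyond ±2 in the SDG arm as well; that cut-off is also an assumption, and it is met in 28–29% of trials.

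| Log-correlation | 0.3 | 0.5 | 0.7 | 0.8 | 0.9 | 0.95 |
|---|---|---|---|---|---|---|
| SD of change | 7.3 | 6.8 | 5.8 | 4.9 | 3.6 | 2.6 |
| Signed-rank within SDG significant | 99% | 94% | 72% | 51% | 27% | 16% |
| Cut-off met and significant (approx.) | 28% | 27% | 22% | 15% | 8% | 5% |

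Across the range the between-arm t-test rejects in 4.6–5.4% and the rank-sum test in 4.7–5.3%. Reporting whichever of those two is significant gives 7–8%. The planned SD of 6 lies between correlations 0.5 and 0.7. The model's selected mean is 5.8%; the documents give the pilot mean as 6.4% (section 3.0) and as 4% (section 11.1).

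**5. The corrected fallback.** Under normality the rank-sum test has relative efficiency 3/π, so power = Φ(2.913 × 0.977 − 1.960) = Φ(0.887) = 81.2%. Simulation gives 80.5–80.6%, against 82.3–82.4% for the t-test in the same runs.

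**The case against.** The strongest reply is that the intent is plain. The paragraph is about comparing SDG with placebo, and signed rank is very probably a slip for rank sum. A within-arm primary analysis would contradict the stated objective, so the large error rates describe a reading that few would adopt. Substituting the rank-sum test by itself costs nothing in type I error.

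The trigger may also never fire. The plan asks whether the Central Limit Theorem holds at this sample size, and in the model above the t-test does keep its level. The cut-off of 2 is not the plan's. The model is also heavier-tailed than the pilot: it implies a median maximum of about 24% in 45 women, against the 16.8% observed, and only about 16% of such samples would stay at or below 16.8%. The 7–8% comes from choosing by p-value, whereas the plan chooses by skewness. For secondary markers, section 11.2 openly accepts more false positives.

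These points limit the weight of the concern. The rates in step 4 show direction, not a measured size. They do not remove the error. The plan prescribes a specific test for the primary endpoint, nothing elsewhere corrects it, and followed as written it does not answer the primary question. Accepting more false positives on secondary markers does not justify a test that omits the comparison.

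**Conclusion.** The concern holds. The default analysis and the sample size are sound; the defect is confined to the skewness fallback and its extension to the secondary markers. Skewness is a real possibility: the plan raises it, and section 3.0 gives a pilot baseline mean of 6.4% against a median of 4%. The documents do not report the skewness of the change itself.

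If the fallback is triggered and run within the SDG arm, a spurious positive result ranges from likely to moderately inflated: 94% to 72% at the correlations that bracket the planned SD of 6, and 16% at the most favourable correlation examined. This rests on the assumed lognormal model and on a literal reading. If the statistician quietly substitutes the rank-sum test, the type I error stays near 5%, and what is lost is prespecification of the primary test. It should be corrected, but it does not threaten the trial as designed.

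**What to change.** In section 11.2, replace the signed-rank test with the two-sample Wilcoxon rank-sum (Mann-Whitney) test on change in Ki-67 from baseline to 12 months, SDG against placebo. State that the same test is the fallback for the secondary markers. Set down the skewness criterion that triggers it before anyone sees unblinded data. A van Elteren version stratified by oral contraceptive use would reflect the randomisation but is optional.

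The cost is one or two lines of wording, with no new data or patients. If the changes turn out to be normal, using the rank-sum test loses about 2 points of power at the planned sample size.

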Specifically, it is hypothesized that SDG administration will be associated with

- a reduction in proliferation as measured by Ki-67;
- a reduction in proportion of specimens with cytologic evidence of atypia;
- a favorable tolerability and quality of life profile;
- no significant impact on menstrual cycle length;
- no significant effect on follicular reserves as measured by early follicular phase anti-mullerian hormone in women entering the study between ages 21-35;
- a reduction in breast pain in those women entering the study with mastalgia.

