3.0 SUMMARY OF STUDY PLAN

The favorable outcome of the pilot study suggests progression to a Phase II multi-institutional placebo-controlled trial of 12 months of Brevail® (50 mg SDG) in moderate and high risk premenopausal women. Modulation of Ki-67 in women with baseline Ki-67 of 2% or greater in hyperplastic tissue is the primary endpoint rather than normalization of atypia, so as to limit the number of women who would need to be screened by RPFNA to 2-3 for every woman going on trial (vs. 4-5 if all had to have atypia). Other risk biomarkers will be measured, as well as impact on quality of life, change in breast pain in those with mastalgia at baseline, and surrogate markers of fertility. These considerations will be important for eventual uptake of SDG as a prevention agent. Mechanisms of action will also be explored. Similar eligibility criteria are used as in the pilot study, where the average percentage of cells expressing Ki-67 at baseline was 6.4% (median 4%) with an average change of -3.7% with a common standard deviation of 5.5%.

The study eligibility is being altered approximately 2.5 years after study start to allow inclusion of women on oral contraceptives. This will both widen application of results should they be positive and is expected to at least double the rate of accrual. Assessment of difference in change in Ki-67 between women randomized to SDG versus placebo can be accomplished with a 2:1 randomization of 242 women. Assuming a dropout rate of 10%, with 220 evaluable subjects there will be 83% power to detect a 2.5% reduction in Ki-67 for the treatment group compared to no reduction in the control group; this will be our primary endpoint. This is based on an assumption of a common standard deviation of 6% for change in Ki-67 in both the no oral contraceptive and oral contraceptive groups and a Type I error rate of 5%

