Evaluation of agent-induced hormonal changes - We will examine whether SDG has any effects on serum levels of bioavailable estradiol, and testosterone, determined at baseline and after 12 months of study medication. We will determine whether addition of SDG alters the frequency or length of menstrual cycles. Effects on follicular reserve will be evaluated with anti-mullerian hormone in a sub-cohort of pre-menopausal women between ages 21 and 35 at study entry. Antimullerian hormone (AMH) is one of the earliest and most sensitive measures of follicular reserve declines for approximately 10 years before the cessation of menses. A distinct advantage for trial purposes is that it does not vary with day of menstrual cycle [119].

Adverse Events and Quality of Life – Change from baseline to 12 months will be assessed for mastalgia (expected in 30-50% of subjects at baseline), menstrual cycle and follicular reserve, and quality of life, as a function of SDG intake, plasma lignan levels and urinary lignan excretion. We will use the breast pain questionnaire (BPQ), which is a modified short form of the McGill Pain questionnaire (SF-MPQ) to assess breast discomfort and the Breast Cancer Prevention Trials (BCPT) Symptom Checklist to monitor quality of life

Correlative analyses will be performed with plasma and urine ENL and total lignans as the independent variable, with modifying variables of baseline BMI age and specific SNPs such as CYP17.

Since this is a phase IIB trial, the power and sample size for the primary endpoint was determined with a two-sided type I error rate of 5%. All subsequent secondary, tertiary and exploratory analyses will also be tested with a two-sided type I error rate of 5%. This may result in an elevated false positive rate for these secondary and tertiary analyses, however, since this is a Phase IIB study, we felt to control the type I error rate for the secondary, tertiary and exploratory analyses would be too conservative.

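### Section 11.2 names no binary method for cytologic atypia; the general rule for secondary endpoints, if applied to it, loses about 13 points of power against a comparison always adjusted for baseline atypia

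*Combined protocol and SAP*

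**What the plan says.** Secondary objective 1 in Section 1.0 is to look for "favorable modulation of other risk biomarkers including cytologic atypia", followed by the serum markers. The specific hypotheses in the same section include "a reduction in proportion of specimens with cytologic evidence of atypia", so the endpoint there is a proportion. In the single-arm pilot, Section 2.4.4.2 reports "A decrease from baseline in the proportion of women with atypical cytology from 62% to 42" percent, with p=0.035.

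Section 11.2 tests the primary endpoint, change in Ki-67, with a two-sample t-test. Analysis of covariance is used only if the arms differ significantly at baseline, and a Wilcoxon Signed Rank test only if skewness is extreme. For the rest it says "For the secondary endpoints, similar methods as above will be used to compare the treatment and control groups at two time points for all markers". The sentence then explains the markers as serum hormones and laboratory tests; atypia is not mentioned. The only binary between-arm test in the section is Fisher's exact test, assigned to grade 3 toxicity or early discontinuation. On error rates: "All subsequent secondary, tertiary and exploratory analyses will also be tested with a two-sided type I error rate of 5" percent.

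Appendix 1, item 5.1, records a five-level cytology category, one level of which is borderline atypia, together with a Masood score. It defines change in the Masood score but does not say which categories count as atypia.

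**The concern.** A statistician who follows the general rule would code atypia 0/1, subtract, and run a t-test on a score that can only be -1, 0 or +1. That score carries the sampling noise of two random aspirates. Adjustment for baseline would depend on a significant baseline difference, which under randomisation occurs in about 1 trial in 20 if the baseline test is at 5% (the plan gives no level for it). The skewness fallback does not help, because a signed rank test is paired and does not compare arms.

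A statistician who reads the rule as limited to blood markers has no stated method at all. The choice of test, and of the categories that count as atypia, would then be open when the data are analysed. Secondary tests are run at an unadjusted 5%, so fixing the method in advance is the main safeguard.

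At stake is a real fall in atypia being reported as non-significant, for a marker whose pilot result is part of the case for this trial.

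**Working it through.** **1. The plan's own figure.** Section 11.1: "A 2:1 randomization of 220 evaluable subjects will provide 83% power to detect a 2.5% reduction in Ki-67 for the treatment group", with an "assumption of a common standard deviation of 6% for change in Ki-67 in both groups". Two-sided 5%, arms of 220/3 and 2×220/3:

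SE = 6 × √(3/220 + 1.5/220) = 0.858; 2.5/0.858 = 2.913; power = Φ(2.913 − 1.96) = 83.0%.

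The stated 83% reproduces. No power is stated for atypia.

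**2. Inputs for atypia.**
- 147 SDG and 73 placebo women (Section 11.1, 2:1 split of 220).
- Baseline 62% in both arms and 42% at 12 months on SDG (pilot, Section 2.4.4.2).
- Placebo stays at 62% (assumption).
- Correlation φ between a woman's two specimens: not in the documents. The pilot's 62% and 42% of 45 women are 28 and 19. With 12 improved and 3 worsened, an exact McNemar test gives 2 × (1+15+105+455)/32,768 = 0.035, matching the reported value. The table is then 16 atypical twice, 14 never, 12 improved and 3 worsened, so φ = (16×14 − 12×3)/√(28×17×19×26) = 188/484.9 = 0.39. This assumes that the pilot used the exact test.

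**3. Closed-form approximation at φ = 0.39, true difference 20 points.** Variances of a single specimen: 0.62×0.38 = 0.2356 and 0.42×0.58 = 0.2436.

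- *Change score.* Placebo variance 2×0.2356×(1 − 0.39) = 0.2874. SDG variance 0.2356 + 0.2436 − 2×0.39×√(0.2356×0.2436) = 0.2923. SE = √(0.2874/73 + 0.2923/147) = 0.0770. Power = Φ(0.20/0.0770 − 1.96) ≈ 74%.
- *12-month value, unadjusted.* SE = √(0.2356/73 + 0.2436/147) = 0.0699. Power = Φ(0.20/0.0699 − 1.96) ≈ 82%; about 80% with the pooled variance of the chi-square test.
- *12-month value adjusted for baseline.* SE shrinks by √(1 − φ²): 0.0699 × √(1 − 0.152) = 0.0644. Power = Φ(0.20/0.0644 − 1.96) ≈ 87%.

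**4. Simulation, 20,000 trials per row.** The adjusted analysis is a logistic regression on arm and baseline atypia.

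| φ | t-test on change | 12-month chi-square | Baseline-adjusted | Loss, change vs adjusted (points) |
|---|---|---|---|---|
| 0 | 52.8% | 80.2% | 80.6% | 28 |
| 0.2 | 61.1% | 80.4% | 82.4% | 21 |
| 0.3 | 67.8% | 80.2% | 84.3% | 17 |
| **0.39** | **73.7%** | **80.1%** | **86.8%** | **13** |
| 0.5 | 81.9% | 80.5% | 90.9% | 9 |
| 0.6 | 89.2% | 79.9% | 94.4% | 5 |

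A repeat simulation at φ = 0.39 gave 73% and 86%. With no treatment effect, all three tests rejected in 4.8% to 5.3% of trials. At φ = 0.39 the change test needs about 1.4 times as many women for the same power.

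**5. Other effect sizes at φ = 0.39.** SDG falling only to 47%: 48% (change) against 63% (adjusted). Placebo also falling, to 52%, with SDG at 42%: 25% against 34%. Power depends heavily on these assumptions; the sample-size ratio stays at about 1.4.

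**The case against.** Four counter-arguments have weight.

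- *The plan does not prescribe a t-test for atypia.* A reader might infer that it does, or that the change test is the only method stated. Neither is supported. The sentence goes on to name blood markers only, and the methods it refers back to include ANCOVA and a Wilcoxon test. Because the plan uses Fisher's exact test for another binary outcome, an analyst might well choose something suitable. This stands: the power loss is conditional on applying the general rule to atypia.
- *The logistic form is not what recovers the power.* Linear ANCOVA on the same 0/1 data gave 87% at φ = 0.39. This stands. The gain comes from always adjusting for baseline, with a method that Section 11.2 already names but makes conditional. The logistic model is preferred because it suits a yes/no outcome.
- *A loss of 20 to 28 points is tempting to quote, but the pilot does not favour it.* With φ near 0, the pilot's p-value would have been about 0.06 to 0.095 under any version of McNemar's test. At φ = 0.2 the exact test gives 0.064; only the uncorrected version, at 0.039, comes near the reported figure. The central estimate is therefore about 13 points.
- *The Masood score is numeric and suits a change analysis.* True, but it does not answer the hypothesis in Section 1.0 about the proportion with atypia.

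The pilot also excluded oral contraceptive users, who are expected to be 72 of the 220 evaluable women, so its rates and correlation may not carry over fully.

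**Conclusion.** The concern holds in a limited form. Section 11.2 assigns no binary between-arm method to the first-named secondary marker. Applying its general rule would cost about 13 points of power (73-74% against 86-87%). At the inferred correlation that rule is also weaker than simply comparing the arms at 12 months (about 80%); the two are roughly equal at φ = 0.5.

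The size rests on three assumptions: pilot rates apply, placebo atypia does not change, and φ is about 0.39. Over φ from 0 to 0.6 the loss is 28 to 5 points, and the adjusted comparison is ahead throughout. There is no bias or type I error problem, and the primary endpoint is not the subject of this point. This is a free improvement to a secondary analysis.

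**What to change.** In Section 11.2, state that:

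1. Atypia at 12 months is analysed as yes/no, listing in advance which categories in Appendix 1, item 5.1, count as atypia and, in particular, on which side borderline atypia falls.
2. The arms are compared by logistic regression on treatment arm, baseline atypia and oral contraceptive stratum, with baseline adjustment always applied whatever the observed baseline balance.
3. The adjusted odds ratio and the risk difference are reported, each with a 95% confidence interval.

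The change-score methods can remain for the continuous markers, including the Masood score. The cost is a few sentences in the plan, ideally settled before unblinding; no extra specimens, visits or women are needed.

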2.4.4.5 Adverse events

The main expected AEs from SDG were diarrhea, flatulence, and irregular menses. GI symptoms, usually grade 1, were encountered in 42%, irregular menses in 26%, and hot flashes in 6% of subjects. Only two grade 3 AEs were reported. One subject was diagnosed with DCIS on the basis of the mammogram performed prior to the 12 month RPFNA. This was not considered related to the study agent. One subject discontinued study after 3 months because of grade 3 pelvic pain that was thought to be possibly related to study agent

Frequency of adverse events by worst reported per subject.

Number	CTC Grade					
	0	1	2	3	4 or 5	Total
Total	7 (14%)	17 (35%)	23 (47%)	2 (4%)	0 (0%)	49

Change in plasma lignans did not correlate with change in Ki-67, adverse events (AEs), or compliance [101].

[figure not shown]

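### The lignan and marker correlations with Ki-67 change are specified without randomised arm, so an all-subject correlation for secondary objective 2 can be significant only because SDG shifts both variables

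*Combined protocol and SAP*

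**What the plan says.** Secondary objective 2 (section 1.0) is "to determine if Ki-67 and modulation of other risk biomarkers is correlated with change in blood or urine lignans".

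Section 11.2 has three pieces of text that bear on it:

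- **Other markers.** "We will also correlate change in the primary biomarker Ki-67 with change in other markers". The examples given are bioavailable estradiol, cytokines and RT-qPCR results, not lignans. The method is Pearson, or Spearman under high skewness. Arm is not mentioned.
- **Lignans.** "Correlative analyses will be performed with plasma and urine ENL and total lignans as the independent variable, with modifying variables of baseline BMI age" and SNPs such as CYP17. Arm is not in the list, and no coefficient or model is named. By content, this is the analysis for objective 2.
- **Regression.** A multiple regression on Ki-67 change takes in age, cytomorphology and Gail risk, "as well as the predictive effect of other biomarkers on modulation of Ki-67". For this model the plan does condition on arm: "Best subsets and stepwise approaches will be employed while controlling for treatment group". Lignans are not named in it.

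Section 6.3.4 also foresees a multivariate analysis of Ki-67 change and lignan levels using SNP results. It does not mention arm.

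On the single-arm pilot, section 2.4.4.5 reports: "Change in plasma lignans did not correlate with change in Ki-67".

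**The concern.** Lignans are measured at baseline and 12 months in both arms. SDG is given in order to raise them, and the trial is powered on SDG lowering Ki-67. Arm is therefore a common cause of both changes. An all-subject correlation mixes two things: any relation between lignan change and Ki-67 change among women on the same treatment, and the difference between arms in the two means. The second is the primary comparison over again.

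If the primary endpoint responds, a significant pooled correlation could be reported as exposure-response or mechanistic support when it carries no information beyond the arm effect. The chance of this rises with the effect of SDG on Ki-67. The pilot makes the case realistic: every woman there took SDG, and no correlation was seen.

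**Working it through.** **Inputs from the documents.** There are 220 evaluable women randomised 2:1, about 147 SDG and 73 placebo. The Ki-67 difference is 2.5 points, SD of change 6, two-sided 5% (11.1, 11.2). An average effect of 1.7 points is the plan's scenario of no efficacy in oral contraceptive users (11.1). Pilot enterolactone (ENL) change on SDG has mean 117.0, SD 117.7 and median 74.8 nmol/L. Pilot baseline SD is 17.4 (2.4.4.1).

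**Assumptions, not in the documents.** Within-arm correlation is zero. Placebo ENL change has mean 0. Its SD is 17.4 (pilot baseline SD) to 24.6 (17.4 × √2), widened to 50 as a sensitivity value.

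**1. Reproduce the stated power.** SE = 6 × √(1/146.67 + 1/73.33) = 0.858. Then 2.5/0.858 = 2.913, and Φ(2.913 − 1.960) = 83.0%. The plan states 83%, so the inputs are read correctly.

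**2. Correlation induced by arm.** With no within-arm association, pooled r = r(arm, Ki-67 change) × r(arm, ENL change). For a binary arm with p = 2/3, √(p(1−p)) = 0.4714.

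- Ki-67: 0.4714 × 2.5 = 1.179. Total SD = √(36 + 1.179²) = 6.115. r = 0.193 in size.
- ENL: 0.4714 × 117 = 55.15. Within-arm variance = (2/3)(117.7²) + (1/3)(24.6²) = 9,437. Total SD = √(9,437 + 55.15²) = 111.7. r = 0.494.
- Product: 0.193 × 0.494 = 0.095 in size, negative in sign.

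**3. Rejection probability.** Fisher z: atanh(0.095) × √217 ≈ 1.40. P(p < 0.05) ≈ Φ(1.40 − 1.96) ≈ 29%.

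**4. Simulation, 10,000 trials per row.** The normal rows use placebo SD 24.6. The skewed rows use lognormal ENL fitted to the pilot medians and means (baseline 11.1 and 15.8; on SDG 99.2 and 132.7), with placebo keeping the baseline distribution. Adjusted tests centre both variables, or their ranks, within arm.

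| Ki-67 arm effect | ENL shape | Pearson, pooled | Spearman, pooled | Either, arm-adjusted |
|---|---|---|---|---|
| 2.5 | normal | 29% | 34% | 5% |
| 2.5 | skewed | 30% | 54% | 5% |
| 1.7 | normal | 17% | 19% | 5% |
| 1.7 | skewed | 17% | 29% | 5% |
| 0 | either | 5% | 5% | 5% |

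**5. Sensitivity.** Here SDG change is normal or lognormal with the pilot mean and SD, and placebo SD runs from 17 to 50. At 2.5 points the ranges are about 28-33% (Pearson) and 30-61% (Spearman). At 1.7 points they are about 16-18% and 17-34%. Spearman is highest with skewed ENL and a narrow placebo spread: about 59% at placebo SD 17, falling to 46% at SD 50. The pilot change is skewed (mean 117.0, median 74.8), and high skewness is when the plan switches to Spearman.

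**6. Other markers.** For assumed standardised arm effects of 0.3, 0.5 and 0.8 SD and a 2.5-point Ki-67 effect, pooled Pearson rejects about 7%, 8-10% and 17%.

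**The case against.** **The documents never say the arms are pooled.** This is correct. Section 11.2 is silent on whether the correlations are pooled, within arm or partial. Pooling is the natural reading where no arm term or subset is named, but it is an inference. What stands is that the choice is left open.

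**Arm is controlled elsewhere.** For estradiol, cytokines and gene expression, the regression in 11.2 is close to an arm-adjusted version of the same question. That is a partial answer. It relies on best-subsets or stepwise selection, omits lignans by name and is not tied to objective 2. The analysis in 6.3.4 names lignans but not arm.

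**The plan accepts extra false positives.** Section 11.2 does so for the number of tests. Confounding of a single test by arm is a different matter.

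**Objective 2 asks only whether the changes are correlated.** If SDG moves both, a marginal correlation exists, and detecting it is not literally an error. It becomes one when it is read as exposure-response. The plan should say which is meant.

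**The inputs are uncertain.** The placebo ENL spread is assumed. Sections 6.3.5 and 6.5.3 anticipate lignan rises in women not on SDG, and 4.3.5 permits flaxseed foods, so lignans need not rise in the active arm alone. A wider placebo spread lowers the Spearman figure. The pilot null, with lignan data on 42 women, is weak evidence that the within-arm correlation is zero.

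**A stronger reading is tempting.** A reader might infer that the treatment effect alone will produce significant correlations across all markers. The figures do not support that. Pearson, the default, misses significance about 70% of the time even at the full design effect. Rejection reaches about half or more only for Spearman with skewed ENL at 2.5 points. For markers that SDG barely moves, the rate stays near 5%.

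**Conclusion.** The concern holds in a limited form. The analyses for objective 2 and the Ki-67/marker correlations are specified without arm. If run on all subjects, they can turn the treatment effect into apparent exposure-response evidence.

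For ENL the false signal is several times the nominal 5% under the plan's own design effect, and it disappears after conditioning on arm. It needs an arm effect on both variables and vanishes if Ki-67 does not respond. The size rests on zero within-arm association, the pilot ENL distribution and the assumed placebo spread. The primary comparison is unaffected. Because the consequence falls on a named secondary objective and the remedy is nearly free, it should be settled before unblinding.

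**What to change.** In section 11.2, state that the lignan correlations for objective 2, and the other correlations of Ki-67 change with marker change, are partial Pearson or Spearman correlations adjusted for randomised arm and oral contraceptive stratum. Report the within-SDG-arm correlation alongside as supportive. Label any pooled unadjusted correlation descriptive, and do not present it as evidence of exposure-response.

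This takes a few lines of text and no new data. There will be fewer nominally significant correlations. The within-SDG estimate uses only about 147 of the 220 women, which is why it should support the adjusted result and not replace it. Once arm is conditioned on, what remains is an observational association without the randomised contrast, and it should be described that way.
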